### 8.2.1 Dose Levels

See [Section 7.0](#) and [Section 7.2](#) for the dosing schema for both arms. **No dose reductions will be made during this study, only dose delays.** Therefore there is only 1 dose level.

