Grade 1	Hold dose pending evaluation. Resume nivolumab/ipilimumab if lymphocytic pneumonitis is excluded.*
Grade 2	Hold until $\leq$ Grade 1*, then restart nivolumab/ipilimumab at same dose.
Grade 3	Off protocol therapy.
Grade 4	Off protocol therapy
*Steroid use does require discontinuation of protocol therapy.	
Recommended management: See Pulmonary Adverse Event Management Algorithm	

Gastritis, nausea, vomiting	Management/Next Dose for Nivolumab and Ipilimumab
Grade 1	Continue protocol therapy*
Grade 2	Hold pending evaluation for gastritis duodenitis and other immune adverse events or other causes. Resume nivolumab/ipilimumab at same dose level after resolution to Grade $\leq$ 1.*
Grade 3	Hold pending evaluation until $\leq$ Grade 1. Resume nivolumab at same dose level.* If symptoms do not resolve within 7 days with symptomatic treatment, patients should go off nivolumab. Discontinue ipilimumab.
Grade 4	Off protocol therapy
*Steroid use does not require discontinuation of protocol therapy.	

Fatigue	Management/Next Dose for Nivolumab and Ipilimumab
Grade 1	Continue protocol therapy.
Grade 2	Continue protocol therapy.
Grade 3	Hold until $\leq$ Grade 2. Resume nivolumab/ipilimumab at same dose level.*
*Steroid use does not require discontinuation of protocol therapy.	

Neurologic events **	Management/Next Dose for Nivolumab and Ipilimumab
Grade 1	Hold dose pending evaluation. Once evaluation is complete, resume nivolumab/ipilimumab at same dose level.*
Grade 2	Hold dose pending evaluation and observation. Hold until $\leq$ Grade 1 and then resume nivolumab/ipilimumab at same dose level.*
Grade 3	Off protocol therapy
Grade 4	Off protocol therapy
*Steroid use does require discontinuation of protocol therapy. **Patients with any grade CNS events of aseptic meningitis, encephalitis, symptomatic hypophysitis, or myopathy, polymyositis, rhabdomyolysis, peripheral demyelinating neuropathy, cranial neuropathy (other than peripheral n. VII), GB syndrome, myasthenia gravis should be off study once diagnosed.	
Recommended management: See Neurologic Adverse Event Management Algorithm	

Endocrine Toxicity**	Management/Next Dose for Nivolumab and Ipilimumab
Grade 1	Continue protocol therapy.*
Grade 2	Hold until $\leq$ Grade 1 and patients are on a stable replacement hormone regimen, then resume nivolumab/ipilimumab at same dose level.*
Grade 3	Off protocol therapy.***

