<math>\leq</math> Grade 1	Hold dose pending evaluation and observation.** Evaluate for signs and symptoms of CHF, ischemia, arrhythmia or myositis. Obtain history EKG, CK (for concomitant myositis), CK-MB. Repeat troponin, CK and EKG 2-3 days. If troponin and labs normalize may resume therapy. If labs worsen or symptoms develop then treat as below. Hold pending evaluation.
Grade >2 with suspected myocarditis	Hold dose.** Admit to hospital. Cardiology consult. Rule out MI and other causes of cardiac disease. Cardiac Monitoring. Cardiac Echo. Consider cardiac MRI and cardiac biopsy. Initiate high dose methylprednisolone. If no improvement within 24 hours, add either infliximab, ATG or tacrolimus. Consult algorithm for more details. Resume therapy if there is a return to baseline and myocarditis is excluded or considered unlikely.
Grade >2 with confirmed myocarditis	Off protocol therapy. Admit to CCU (consider transfer to nearest Cardiac Transplant Unit). Treat as above. Consider high dose methylprednisolone. Add ATG or tacrolimus if no improvement. Off treatment.
*Including CHF, LV systolic dysfunction, Myocarditis, CPK, and troponin	
**Patients with evidence of myositis without myocarditis may be treated according as “other event”	
Note: The optimal treatment regimen for immune mediated myocarditis has not been established. Since this toxicity has caused patient deaths, an aggressive approach is recommended.	

ALL OTHER EVENTS (Note 1)	Management/Next Dose for Nivolumab and Ipilimumab
≤ Grade 1	No change in dose
Grade 2	Hold until ≤ Grade 1, then resume nivolumab/ipilimumab at same dose level.
Grade 3	Off protocol therapy (exceptions noted below in note 2)
Grade 4	Off protocol therapy

Note: 1. Modifications are applicable to toxicity that is deemed related to study drug (attribution of possible, probable, or definite).
 
Note 2. For any grade 2 drug-related uveitis or eye pain or blurred vision that does not respond to topical therapy and does not improve to Grade 1 severity within the re-treatment period OR requires systemic treatment, nivolumab and ipilimumab should be discontinued.
	
Recommended management: As clinically indicated	

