Adverse Events with Possible Relationship to BMS-936558 (Nivolumab, MDX-1106) (CTCAE 5.0 Term) [n= 2069]			Specific Protocol Exceptions to Expedited Reporting (SPEER)
Likely (>20%)	Less Likely (<=20%)	Rare but Serious (<3%)	
	Diarrhea		Diarrhea (Gr 3)
	Dry mouth		Dry mouth (Gr 2)
		Gastritis	
		Mucositis oral	
	Nausea		Nausea (Gr 2)
	Pancreatitis 		
GENERAL DISORDERS AND ADMINISTRATION SITE CONDITIONS			
Fatigue			Fatigue (Gr 3)
	Fever		Fever (Gr 2)
	Injection site reaction		Injection site reaction (Gr 2)
IMMUNE SYSTEM DISORDERS			
		Allergic reaction 	
		Autoimmune disorder 	
		Cytokine release syndrome 	
		Immune system disorders - Other (GVHD in the setting of allotransplant) 	
		Immune system disorders - Other (sarcoid granuloma) 	
INJURY, POISONING AND PROCEDURAL COMPLICATIONS			
	Infusion related reaction 		
INVESTIGATIONS			
	Alanine aminotransferase increased 		Alanine aminotransferase increased (Gr 3)
	Aspartate aminotransferase increased 		Aspartate aminotransferase increased (Gr 3)
	Blood bilirubin increased 		Blood bilirubin increased (Gr 2)
	Creatinine increased		
	Lipase increased		
	Lymphocyte count decreased		Lymphocyte count decreased (Gr 2)
	Neutrophil count decreased		
	Platelet count decreased		
	Serum amylase increased		
METABOLISM AND NUTRITION DISORDERS			
	Anorexia		
		Hyperglycemia	Hyperglycemia (Gr 2)
		Metabolism and nutrition disorders - Other (diabetes mellitus with ketoacidosis) 	
MUSCULOSKELETAL AND CONNECTIVE TISSUE DISORDERS			
	Arthralgia		
		Musculoskeletal and connective tissue disorder - Other (polymyositis)	
		Myositis	
		Rhabdomyolysis	
NERVOUS SYSTEM DISORDERS			
		Encephalopathy 	
		Facial nerve disorder 	

Adverse Events with Possible Relationship to BMS-936558 (Nivolumab, MDX-1106) (CTCAE 5.0 Term) [n= 2069]			Specific Protocol Exceptions to Expedited Reporting (SPEER)
Likely (>20%)	Less Likely (<=20%)	Rare but Serious (<3%)	
		Guillain-Barre syndrome 	
		Myasthenia gravis 	
		Nervous system disorders - Other (demyelination myasthenic syndrome)	
		Nervous system disorders - Other (encephalitis) 	
		Nervous system disorders - Other (meningoencephalitis)	

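### Two footnotes in Section 8.2.2 give conflicting dosing rules for drug-related Grade 1–2 muscle inflammation without myocarditis

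*Combined protocol and SAP*

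**What the plan says.** Three parts of Section 8.2.2 bear on muscle inflammation.

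- **Cardiac table.** The lowest-grade row tells sites to "Evaluate for signs and symptoms of CHF, ischemia, arrhythmia or myositis" and to measure CK. The second footnote adds: "Patients with evidence of myositis without myocarditis may be treated according as" an other event.
- **All Other Events table**, which follows directly. At Grade 1 or below the instruction is "No change in dose". At Grade 2 it is "Hold until ≤ Grade 1, then resume nivolumab/ipilimumab at same dose level". At Grade 3 it is "Off protocol therapy (exceptions noted below in note 2"), and Grade 4 is also off therapy. Note 1 limits the table to toxicity considered at least possibly drug-related. Note 2 deals only with eye events.
- **Neurologic events table, second footnote.** It covers any-grade events on a list that starts with meningitis, encephalitis and hypophysitis and goes on: "or myopathy, polymyositis, rhabdomyolysis, peripheral demyelinating neuropathy, cranial neuropathy (other than peripheral n. VII), GB syndrome, myasthenia gravis should be off study once diagnosed".

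Section 8.2.1 adds that "No dose reductions will be made during this study, only dose delays".

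**The concern.** A patient with low-grade drug-related muscle inflammation and no myocarditis appears to fall under two rules that lead to different dosing. One permits treatment to continue, or to resume after a hold. The other ends it. Neither footnote refers to the other, and no order of precedence is given.

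This is a safety rule for events that the nivolumab risk list classes as rare but serious. With no lower dose available, the choice is between re-exposure at full dose (both drugs, for a patient still on the combination) and permanent removal. Two sites could each follow the protocol and act differently on the same event. The term a site happens to record could decide the outcome.

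**Working it through.** The point rests on text, so there is no plan figure to reproduce. The check compares the two rules grade by grade and then looks for anything that reconciles them.

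**1. Where the cardiac footnote leads.** Its phrase matches the heading of the next table, All Other Events. Because of Note 1 of that table, the comparison is limited to drug-related events.

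**2. How far the neurologic footnote reaches.** It opens with any-grade CNS events. However, myopathy, polymyositis, rhabdomyolysis, Guillain-Barré syndrome and myasthenia gravis are not CNS events, and they share the same verb. The natural reading is that any grade applies to the whole list.

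**3. Comparison for diagnosed drug-related muscle inflammation, myocarditis excluded.**

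| Grade | Cardiac footnote, via All Other Events | Neurologic footnote | Result |
|---|---|---|---|
| 1 | continue unchanged | off | conflict |
| 2 | hold, then resume at the same dose | off | conflict |
| 3 | off | off | agree |
| 4 | off | off | agree |

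The rules conflict at 2 of 4 grades.

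**4. Whether the terms keep the rules apart.** The nivolumab list (Section 9.4.1) carries "Musculoskeletal and connective tissue disorder - Other (polymyositis"), myositis and rhabdomyolysis as three separate entries. The ipilimumab list (Section 9.4.2) carries polymyositis but no bare myositis. The neurologic footnote uses *myopathy* without qualification, and that word ordinarily includes inflammatory muscle disease. The protocol gives no criterion for separating these terms when dosing.

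**5. Whether a general rule settles it.** Section 8.2 stops treatment when immunosuppression beyond steroids is needed, when a hold exceeds 6 weeks, or after more than two delays for the same event. It also bars restart until steroids are down to 5 mg prednisone equivalent. None of these decides a first Grade 1–2 episode that settles within 6 weeks on steroids or less. The advice before the tables to follow event-specific guidance does not help either, since both footnotes are event-specific.

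**6. Steroid rules.** The Neurologic table says steroid use requires discontinuation. The All Other Events table has no steroid footnote, so the general 5 mg restart rule applies. A steroid-treated Grade 2 case therefore diverges on this count too.

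**7. Example.** Take Grade 2 drug-related muscle inflammation with raised CK and weakness, myocarditis excluded. Recorded as myositis, treatment may resume once the event is at Grade 1 or below. Recorded as polymyositis or myopathy, treatment ends.

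**The case against.** The best defence is that the footnotes address different events. Only the cardiac footnote prints *myositis*; the neurologic footnote names other diagnoses, and the nivolumab list keeps them as separate entries. The triggers differ as well: evidence of myositis found in a cardiac work-up, against an established diagnosis. The cardiac wording is permissive, so a site that stops treatment complies with both. The destination table is residual, so a diagnosis already named elsewhere is arguably not an other event. Finally, retreatment would be subject to the Section 8.2 safeguards and, in the lowest cardiac grade row, to an initial hold for evaluation.

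Part of this stands. The conflict arises through overlapping terms, not through one word appearing in both places. The footnotes do not command opposite actions: one permits what the other bars. The safeguards do limit re-exposure.

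It does not remove the problem. A site that resumes can point to express permission, and a site that stops can point to an express directive. The cardiac footnote itself sends myositis to the residual table, so the heading of that table cannot exclude it. The distinction between evidence and diagnosis is sensible, but the protocol does not draw it: myositis that has been diagnosed is also evident.

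**Conclusion.** The concern holds. For drug-related muscle inflammation without myocarditis, Section 8.2.2 supports two incompatible courses at Grades 1 and 2 and a single course at Grades 3 and 4. It should be corrected because it is a contradiction in a stated safety rule, and the cardiac work-up itself leads sites to it.

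The conclusion rests on three readings: that the other-event wording means the All Other Events table, that any grade covers the whole neurologic list, and that unqualified myopathy includes inflammatory muscle disease.

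The number of patients affected is small and cannot be sized. The nivolumab list puts myositis, polymyositis and rhabdomyolysis in its below-3% category. The ipilimumab list puts polymyositis in its category of up to 20%, but that term is named outright in the neurologic footnote, so the figure does not size the ambiguous group. Neither list gives rates by grade or separates cases without myocarditis. The count could be zero. No endpoint, sample size or analysis is affected.

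**What to change.** Amend the cardiac footnote to name the governing rule, for example: *Patients with diagnosed myositis, myopathy, polymyositis or rhabdomyolysis without myocarditis follow the Neurologic events footnote (off protocol therapy at any grade). CK elevation without a diagnosed muscle disorder may be handled under All Other Events.* Add *myositis* to the neurologic list so that the terms match. In the same edit, the neurologic footnote could say off protocol therapy in place of off study, in line with the tables.

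The stricter direction fits Appendix IV, which names polymyositis and rhabdomyolysis among the histories to exclude because of the risk of recurrence or exacerbation. The direction remains the sponsor's clinical choice. If retreatment at Grades 1–2 is intended, narrow the neurologic footnote explicitly for these muscle diagnoses and cross-refer to the cardiac footnote.

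The cost is a short edit to each of two footnotes, with no added data or procedures. Under the stricter option, a few patients with low-grade myositis who might have been retreated would stop therapy.

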For RCC results have been reported.[43] Pts were randomized to nivolumab 3mg/kg + ipilimumab 1mg/kg (n=21) and nivolumab 1mg/kg + ipilimumab 3mg/kg (n=23). Most pts (n=34; 77%) had prior systemic therapy (N3 + I1: 16; N1 + I3: 18). Objective response rate (ORR) was 29% (nivolumab 3mg/kg + ipilimumab 1mg/kg) and 39% (nivolumab 1mg/kg+ ipilimumab 3mg/kg.) Duration of response was 4.1 to 22.1 weeks (all 6 responses ongoing) in

nivolumab 3mg/kg + ipilimumab 1mg/kg, and 6.1 yo 18.3 weeks (8/9 responses ongoing) in nivolumab 1mg/kg+ ipilimumab 3mg/kg. Responses occurred by first tumor assessment at week 6 in 67% of responding patients in both patient cohorts. Stable disease was seen in 7 (33%) patients (nivolumab 3mg/kg + ipilimumab 1mg/kg) and 9 (39%) patients (nivolumab 1mg/kg + ipilimumab 3mg/kg). Treatment-related adverse events (AEs) were seen in 89% of patients with 16% discontinuation due to any-grade related AEs. Grade 3–4 related AEs 43%, most commonly ↑ lipase (16%, n=7), ↑ ALT (11%, n=5), diarrhea (9%, n=4), colitis (5%, n=2), ↑ amylase (5%, n=2). No grade 3–4 pneumonitis was seen. Based on the above background trials, the combination is being evaluated in other disease settings typically with 3mg/kg nivolumab and 1mg/kg ipilimumab q 3 weeks during induction, for 4 doses. This is the induction dosing we have chosen for the combination arm of the trial.

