### 8.2.2 Dose Modification

Skin Rash and Oral Lesions	Management/Next Dose for Nivolumab and Ipilimumab
Grade 1	Continue on protocol therapy*
Grade 2	Continue on protocol therapy.*
Grade 3	Hold** until ≤ Grade 1. Resume nivolumab/ipilimumab at same level*
Grade 4	Off protocol therapy
*Steroid use does not require discontinuation of protocol therapy.	
**Any grade Steven Johnson syndrome requires discontinuation of protocol therapy.	
Recommended management: See Skin AE management algorithm	

Liver Function ALT AST Bilirubin	Management/Next Dose for Nivolumab and Ipilimumab
Grade 1	Continue protocol therapy*
Grade 2	Hold therapy until ≤ grade 1 then restart nivolumab/ipilimumab at same dose.*
Grade 3	Off protocol therapy
Grade 4	Off protocol therapy
*Steroid use does require discontinuation of protocol therapy.	
Recommended management: see Hepatitis AE management algorithm	

Colitis**	Management/Next Dose for Nivolumab and Ipilimumab
Grade 1	Continue protocol therapy*
Grade 2	Hold therapy until $\leq$ Grade 1*, then restart nivolumab at same dose. Discontinue ipilimumab.
Grade 3	Off protocol therapy.
Grade 4	Off protocol therapy.
See GI AE Algorithm for management of symptomatic colitis. *Steroid use does not require discontinuation of protocol therapy. **Follow this table for diarrhea when the workup shows objective evidence of autoimmune colitis.	
Recommended management: see GI AE management Algorithm	

Diarrhea**	Management/Next Dose for Nivolumab and Ipilimumab
Grade 1	Continue protocol therapy
Grade 2	Hold until $\leq$ Grade 1*, then restart nivolumab/ipilimumab at same dose.
Grade 3	Hold until $\leq$ Grade 1*, then restart nivolumab/ipilimumab at same dose.
Grade 4	Hold until $\leq$ Grade 1*, then restart nivolumab/ipilimumab at same dose.
*Steroid use does not require discontinuation of protocol therapy. **Follow this table for diarrhea when the workup shows no objective evidence of autoimmune colitis	

Pancreatitis**	Management/Next Dose for Nivolumab and Ipilimumab
Grade 2	Continue on protocol therapy*
Grade 3	Hold therapy until $\leq$ grade 2 then restart nivolumab/ipilimumab at same dose.*
Grade 4	Off protocol therapy
*Steroid use does require discontinuation of protocol therapy. **Patients who have asymptomatic amylase or lipase elevation may have a self-limited course and may continue therapy.	

Pneumonitis	Management/Next Dose for Nivolumab and Ipilimumab

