All other Grade  $\geq$  3 events including anemia, hyponatremia, hypernatremia, hypokalemia, hyperkalemia, hypocalcemia, hypercalcemia, hypomagnesemia, hypermagnesemia, hypoglycemia, hyperglycemia, elevated amylase or lipase that is deemed unrelated to drug (attribution of unrelated or unlikely) does not require change in dose.

Lymphopenia of any grade does not require change in dose.

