## Hepatic Adverse Event Management Algorithm

Rule out non-inflammatory causes. If non-inflammatory cause, treat accordingly and continue I-O therapy. Consider imaging for obstruction.

[figure not shown]
Patients on IV steroids may be switched to an equivalent dose of oral corticosteroids (e.g. prednisone) at start of tapering or earlier, once sustained clinical improvement is observed. Lower bioavailability of oral corticosteroids should be taken into account when switching to the equivalent dose of oral corticosteroids.

\*I-O therapy may be delayed rather than discontinued if AST/ALT ≤ 8 x ULN and T.bili ≤ 5 x ULN.

\*\*The recommended starting dose for grade 4 hepatitis is 2 mg/kg/day methylprednisolone IV.

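### Section 8.2.2 both allows continuing and requires stopping for drug-related, asymptomatic Grade 3-4 lipase or amylase elevation, and Note 2 lacks the Grade 3 exceptions it is cited for

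*Combined protocol and SAP*

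**What the plan says.** **Lipase and amylase (Section 8.2.2).** The second footnote to the pancreatitis table says: "Patients who have asymptomatic amylase or lipase elevation may have a self-limited course and may continue therapy". It names no grade and no attribution. Further on, the ALL OTHER EVENTS table has a Grade 3 row that reads "Off protocol therapy (exceptions noted below in note 2"), and a Grade 4 row that also ends protocol therapy. Note 1 sets that table's scope: "Modifications are applicable to toxicity that is deemed related to study drug (attribution of possible, probable, or definite"). The paragraph after the table opens with other events of Grade 3 or above, lists several laboratory abnormalities, and ends with "elevated amylase or lipase that is deemed unrelated to drug (attribution of unrelated or unlikely) does not require change in dose". The next line exempts lymphopenia whatever its grade.

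**Note 2.** It concerns Grade 2 drug-related uveitis, eye pain or blurred vision that fails topical therapy or needs systemic treatment, and it tells the site to stop both drugs.

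**Liver (Section 8.2.2 and Appendix III).** The liver table takes Grades 3 and 4 off protocol therapy and then adds "Recommended management: see Hepatitis AE management algorithm". A footnote to the hepatic algorithm in Appendix III states: "I-O therapy may be delayed rather than discontinued if AST/ALT ≤ 8 x ULN and T.bili ≤ 5 x ULN".

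**The concern.** Lipase is a scheduled test. Section 5.0, footnote B, asks for it every 4 weeks four times in Arm 1, and every 3 weeks four times and then once more in Arm 2 and after crossover. High values without symptoms will therefore be found. Amylase is not on the calendar and will be seen only where a site orders it. AST, ALT and bilirubin are in the chemistry panel at every treatment visit.

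A site with a drug-related, asymptomatic Grade 3 lipase value can follow one passage and keep treating, or follow another and end treatment for good. Two sites acting in good faith could do opposite things. That makes safety handling uneven and can change drug exposure inside the 6-month window for the primary endpoint. In Arm 1 a removal of this kind also closes crossover, because Section 3.4.2 excludes patients taken off for reasons other than progression. The LPS and UPS/MFH arms are declared promising on 2 responses among 12 patients (Section 13.3.2), so the handling of a single patient could matter there.

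**Working it through.** **Step 1. Lipase/amylase passages side by side.**

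| Situation | Pancreatitis footnote | ALL OTHER EVENTS table, Note 1 and following paragraph | Conflict? |
|---|---|---|---|
| Unrelated to drug, asymptomatic, Grade 3-4 | may continue | no change in dose | No |
| Drug-related, asymptomatic, Grade 3 | may continue | off therapy, subject to Note 2 | Yes |
| Drug-related, asymptomatic, Grade 4 | may continue | off therapy | Yes |
| Symptomatic pancreatitis | not covered; the table's own rows apply | not needed | No |

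The right-hand entries for related events follow in three moves. The closing paragraph places raised amylase or lipase among the other events of Grade 3 or above. It exempts only the unrelated ones. Note 1 says the table is for related ones. So a related elevation goes to the Grade 3 or Grade 4 row.

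This reading has an odd consequence. A related, symptom-free Grade 3 lipase value ends treatment, while Grade 3 pancreatitis in its own table is held and restarted (unless steroids are used).

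**Step 2. The pointer.** The Grade 3 row sends the reader to Note 2 for exceptions. Note 2 deals with Grade 2 eye events and adds a reason to stop. It contains no Grade 3 exception. The one exception nearby that reaches Grade 3 for related events is lymphopenia, and it stands in the text after the table.

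**Step 3. Liver.** By grade alone, the liver table discontinues only at Grades 3 and 4, so a footnote offering delay in place of discontinuation appears to reach into Grade 3. This is an inference: the algorithm figure is not reproduced, the footnote's anchor cannot be seen, and the documents print no grade cut-offs in multiples of ULN.

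**Step 4. How often such events might arise.** Section 1.6 gives the denominators: "Pts were randomized to nivolumab 3mg/kg + ipilimumab 1mg/kg (n=21) and nivolumab 1mg/kg + ipilimumab 3mg/kg (n=23"), so N = 21 + 23 = 44. It gives the most common Grade 3-4 related events as "lipase (16%, n=7), ↑ ALT (11%, n=5), diarrhea (9%, n=4), colitis (5%, n=2), ↑ amylase (5%, n=2"). The printed percentages reproduce:

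- lipase 7/44 = 15.9% (exact 95% interval 6.6% to 30.1%)
- ALT 5/44 = 11.4% (3.8% to 24.6%)
- amylase 2/44 = 4.5% (0.6% to 15.5%)

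Assume these rates carry over to the planned evaluable combination patients, 38 + 12 + 12 + 24 = 86, not counting crossover patients:

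- lipase 86 × 7/44 = 13.7 (5.7 to 25.9 across the interval)
- ALT 86 × 5/44 = 9.8 (3.3 to 21.1)
- chance of at least one Grade 3-4 lipase event in a 12-patient arm: 1 − (37/44)^12 = 87.5%. At the interval ends it is 1 − (1 − 0.066)^12 = 56% and 1 − (1 − 0.301)^12 = 99%.

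These count all Grade 3-4 related events. The documents do not split them by symptoms, by Grade 3 against Grade 4, or by multiple of ULN, so the subset in conflict cannot be derived.

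**The case against.** **The specific rule governs.** ALL OTHER EVENTS is by name a residual table, and asymptomatic amylase or lipase elevation is already dealt with in the pancreatitis footnote. The closing paragraph speaks only of unrelated elevation and never says outright that related elevation must stop. This is the best defence. It is undercut because the same paragraph puts raised amylase and lipase among the other events and attaches the exemption to attribution. If the footnote covered every asymptomatic case, that entry would add nothing for them. The defence does narrow the conflict to drug-related, asymptomatic Grade 3-4 elevation.

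**The liver passages are already ranked.** The sentence introducing the Section 8.2.2 tables calls them protocol-specific instructions, while Section 8.1 calls the algorithms recommended guidelines. The liver table's reference can be read as advice on treating the event, with the table deciding on study drug. These labels favour the table, and the footnote allows delay, not uninterrupted dosing. Much of this stands. What remains is that the table itself sends the site to the algorithm and no sentence states precedence.

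**The pointer is a misplaced cross-reference.** The lymphopenia line makes that plausible. It would be wrong to infer that no exception reaching Grade 3 exists anywhere. What holds is that none is in Note 2.

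**Effect on the endpoint.** Patients who began treatment stay evaluable in their randomized arm (Section 13.3), so removal does not drop them from the denominator. The effect through lost exposure is plausible but not quantified.

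**Conclusion.** The conflict is real for drug-related, asymptomatic Grade 3-4 lipase or amylase elevation, and the Note 2 pointer leads to no Grade 3 exception. Both follow from printed text and rest on no missing figure or assumed rate. The liver point is secondary: it is an unstated order of precedence, with an inferred overlap with Grade 3.

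A reader might infer that every Grade 3-4 lipase or ALT event falls under opposing rules. The documents do not support that. Unrelated lipase elevation is treated consistently, symptomatic pancreatitis has its own rows, and the hepatic allowance ends at its stated AST/ALT and bilirubin limits. A reader might also take the Section 1.6 rates as a ceiling on the number affected. They are point estimates from 44 renal-cancer patients, of whom only 21 had this trial's induction doses, and the lipase interval runs up to 30.1%. They show that such events are likely and no more. The number in conflict is unknown.

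This should be corrected because it concerns a stopping rule triggered by a scheduled test. It does not undermine the statistical design.

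**What to change.** 1. In Section 8.2.2, reconcile the pancreatitis footnote with the ALL OTHER EVENTS table and the paragraph after it, so that one instruction covers drug-related, asymptomatic Grade 3-4 lipase or amylase elevation, with its grade and attribution limits stated.
2. Correct, complete or delete the Grade 3 row's reference to Note 2. If the lymphopenia line is the intended exception, point to it.
3. Add one sentence saying whether the Section 8.2.2 tables or the Appendix III algorithms take precedence on continuing study drug, and whether the hepatic footnote applies in this trial.

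Which rule applies is the sponsor's clinical decision; the request is only that the passages agree. The cost is a wording change in Section 8.2.2 and, if needed, Appendix III, with no new procedures and no change to sample size or analysis.
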